The objective of this study is to evaluate which pulse rate (frequency) is the most efficacious in transcutaneous electric nerve stimulation (TENS) as a therapeutic option for pelvic pain. The

proposed study will be a randomized clinical trial. There will be three treatment arms with no sham or control:

- 1. Group1: TENS frequency is set to 20 Hz
- 2. Group2: TENS frequency is set to 50 Hz
- 3. Group3: TENS frequency is set to 100 Hz

The study will be conducted for a total of 4 weeks (28 days, including the data for the week prior to the initial consent, week 1), followed by a 90-day observational period.

1. Baseline Measurement of chronic pain using the VAS and GUPI with baseline treatment for 7 days [Week 1 (at first visit, data from week prior) then at Week 2 as a control period]

2. Active measurement of chronic pain using the VAS and GUPI as well as weekly usage logs during TENS treatment for 2 weeks [Week 3-4]

3. Durability: We will again collect data at 1, 2, and 3 months after the week visit for those who elect to continue, repeating the VAS and GUPI and treatment inventory, asking how much the TENS has been used and at what setting, to assess durability and observe participant-directed settings.

RANDOMIZATION

Subjects will be randomly assigned with equal probability to one of the three study groups. Randomization will utilize a web site (www.randomization.com) to provide randomization. Randomization will occur in blocks so that if the study needs to be terminated early there is an equal number of participants in each group at the time of termination. Also, we will stratify groups by gender so that there is an equal number of participants from each gender in each group to help limit this confounding variable. Allocation-concealment will be achieved by using sealed envelopes opened only after subjects are enrolled. Record keeping will be from participant responses via Qualtrics before and during TENS treatment. The scoring of the VAS and GPI scales, the compliance rate (used TENS or not), and any participant comments are recorded. Participant demographic will include age, gender, and pertinent urological history, if any.

BLINDING

There will be single blinding. Study participants/caretakers will not know which frequency has been assigned.

INTENTION-TO-TREAT

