Statistical Methods

For the primary objectives:

- Analysis of variance with a fixed effect of treatment with Tukey's multiple comparison test will be used to test for differences in the reduction in genitourinary symptoms among the three treatment arms. Reduction will be parameterized as a relative change from baseline to after the two weeks of treatment. VAS pain response before and after treatment will be compared among the three groups using repeated measures ANOVA with Tukey's multiple comparison tests.
- The Chi-square test or Fisher's exact test, as appropriate, will be used to compare the rates of response among the three treatment arms at the end of the 14-day treatment period.

For the secondary objectives, a repeated measures analysis of variance will be used to analyze the outcomes of interest on a week-to-week basis (improvement in GUPI scores). A treatment-by-time interaction will be examined to determine if the patterns of change in GUPI and VAS scores over time differ across groups. Adjusted pairwise comparisons (Tukey or Bonferroni method) will be used to compare treatment groups to one another.

Data transformations may be applied, if necessary, in order to meet the required standard model assumptions.

Sample Size Considerations

Power: The number of participants needed was based on a power calculation (ANOVA with 2-tailed alpha of 0.05) assuming that the minimally important difference to detect among the three groups in the change in VAS score would be at least one within-group standard deviation of the change in score at 14 days. With 21 participants per group the power is estimated at 81%. We propose to randomize 25 per group assuming the dropout rate may be as high as 20%.

Based on investigator expertise and some published studies, we assume that the proportions of responders based on our criteria of a “favorable response” for each of the three TENS groups will be around 40 % (1,2,4,7,10). In our study we are aiming for at least a 40% response rate in our complex and refractory population.

Conduct of the study

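### Repeated measures ANOVA with no missing-score method wastes Week 3 data and can distort arm contrasts; a mixed model on all randomised participants would serve better

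*Combined protocol and SAP*

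**What the plan says.** All references are to the combined protocol and SAP.

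- **Statistical Methods, primary objectives:** "VAS pain response before and after treatment will be compared among the three groups using repeated measures ANOVA", with Tukey comparisons.
- **Statistical Methods, secondary objectives:** "a repeated measures analysis of variance will be used to analyze the outcomes of interest on a week-to-week basis", with a treatment-by-time interaction.
- **Sample Size Considerations:** the calculation is an "ANOVA with 2-tailed alpha of 0.05" for a difference of "at least one within-group standard deviation of the change in score at 14 days". It continues "With 21 participants per group the power is estimated at 81" per cent, then "We propose to randomize 25 per group assuming the dropout rate may be as high as 20" per cent. Dropout is used only to set the number randomised.
- **Intention-to-Treat:** all subjects are to be analysed by that principle, but the set is limited to those with at least 8 documented sessions.
- **Conduct of the study; E. Risks:** participants with severe or persistently worsening symptoms are removed and counted as treatment failures. Those with skin irritation from the pads are taken off the study.

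Nowhere does the document give a likelihood-based model, an imputation method, a rule for a missing weekly VAS or GUPI score, or a sensitivity analysis for dropout.

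**The concern.** Classical repeated measures ANOVA needs a score at every time point in the model. A participant who gives a Week 3 score and then leaves contributes nothing, although that score is informative about the missing Week 4 value. The deletion is harmless for the arm contrasts only if leaving is unrelated to response, or related in a way that leaves the contrasts intact. Here some removals are triggered by worsening symptoms. Counting those participants as failures can feed the responder comparison, but it supplies no VAS or GUPI score for the ANOVA.

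At stake are the precision of a primary outcome in a trial sized with little slack, and the validity of the comparison between frequencies.

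**Working it through.** **1. The plan's power figure.** Inputs from Sample Size Considerations: three arms, alpha 0.05, largest difference 1 SD, 21 per arm. With means 0, 0.5 and 1 SD (the middle mean is my assumption), the noncentral F calculation gives 81.5%, which reproduces the stated 81%.

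**2. Dropout alone.** 25 × 0.80 = 20 per arm, 60 of 75. The same calculation gives 79.3%.

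**3. Which forms are at risk.** Week 1 scores decide eligibility, and Week 2 scores are handed in at the in-person visit where the frequency is allocated (Study Procedures). Only the Week 3 and Week 4 forms fall after allocation. Let m be the chance that a remaining participant misses one form; the document gives no value, so I take 0.03, 0.05 and 0.10.

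| m | Primary VAS, two time points: 75 × 0.8 × (1−m) | Weekly analysis: 75 × 0.8 × (1−m)² |
|---|---|---|
| 0.03 | 58.2 | 56.5 |
| 0.05 | 57.0 | 54.2 |
| 0.10 | 54.0 | 48.6 |

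The weekly column is about 16 to 19 per arm. The plan's own ANOVA calculation gives 68.6% power at 16 per arm and 77.0% at 19.

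**4. Distortion when the arms truly differ.** Simulation with assumed inputs: one Week 3-based removal rule in all arms, 20% missing overall, true best-to-worst difference 1 SD. Complete cases recovered about 0.80-0.90 SD; a likelihood estimate using Week 3 recovered about 1.00. Over a wider set of assumptions (correlation 0.5-0.8) complete cases recovered 0.68-0.97 SD. The weakest arm loses more of its poor responders, so the contrast shrinks. This needs leaving to track response: if it depended on the Week 3 level alone and all weeks were equally correlated at r, the covariance of that level with the Week 4 change from baseline would be proportional to r − r = 0, and there would be no shrinkage.

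**5. Distortion when the arms do not differ.** Assumed VAS SD 2, between-week correlation 0.4-0.8.

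- Equal 20% dropout in every arm: no between-arm bias under either method.
- Dropout of 8%, 20% and 32% across the arms, related to Week 3 response: complete cases show a false advantage of 0.08-0.21 VAS points for the arm losing most; the likelihood estimate is within 0.03 of zero.
- The same unequal dropout driven by the unseen Week 4 score: bias of 0.38-0.68 with complete cases and 0.36-0.62 with the likelihood method.

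**6. The 8-session rule.** At one session a day, anyone stopping by the end of Week 3 has at most 7 sessions and is excluded under any model.

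**The case against.** Five points deserve weight.

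- **Deletion is inferred.** The plan does not say complete-case, and the name is sometimes used for a mixed model. This stands, but it leaves the model unspecified, which is itself a reason to name it.
- **The loss is easily overstated.** A reader might treat all four weekly forms as at risk, 0.8 × (1−m)⁴, and arrive at 39-53 of 75. The visit schedule does not support that, because Weeks 1-2 precede allocation. Nor does a missed Week 3 form remove anyone from a two-time-point primary VAS analysis. The 20% is also stated as an upper limit.
- **Differential dropout is not documented.** A reader might infer that the analysis will favour the arm whose poor responders leave. All arms share the device, site and schedule, and participants are blinded to frequency. A false difference under the null needs outcome-related dropout that differs by arm, and the document gives no evidence of it.
- **The ANOVA is not the main departure from intention-to-treat.** The 8-session rule excludes early leavers first. The ANOVA adds those who leave after 8 or more sessions and those who miss single forms.
- **A mixed model is no cure for unseen deterioration.** This stands: step 5 shows almost no gain in that case.

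What survives is that collected Week 3 scores would be discarded in a trial whose removals are partly outcome-related, when a standard method uses them.

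**Conclusion.** The concern holds in a limited form, and the plan should be changed. The named method, classically fitted, leaves about 54-58 of 75 for the primary VAS comparison and 49-56 for the weekly analyses, if 3-10% of Week 3-4 forms are missed on top of 20% dropout. Much of the loss is already budgeted: dropout alone takes power from 81% to 79%, and missed forms take the weekly analysis to about 69-77%. Possible distortion of the contrasts matters more. Its size rests on assumed correlations and removal rules, so the 0.8-0.9 SD figure illustrates the direction and rough scale and is not a forecast. The documents do not establish that bias will occur, or that it would favour a particular frequency.

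**What to change.** 1. In Statistical Methods, replace repeated measures ANOVA for VAS and GUPI with a linear mixed model for repeated measures: REML, unstructured covariance, with terms for arm, week, arm-by-week, baseline score and the gender stratum. Include every randomised participant with any post-baseline score, and take the Week 4 arm contrasts from it with Tukey adjustment.
2. In Intention-to-Treat, delete the 8-session condition from that set and keep it for the per-protocol set. Otherwise early leavers with a Week 3 score stay excluded whatever model is used.
3. State how VAS and GUPI scores are treated after removal for worsening symptoms or skin irritation, alongside the failure rule for the responder outcome.
4. Add a sensitivity analysis for dropout that depends on unseen scores, because the mixed model assumes data are missing at random.

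The cost is SAP wording and slightly more analysis work, with no extra data. The change cannot restore Week 4 scores that were never collected.

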Study	Frequency (Pulse Rate, Hz)	Width (Pulse Width, Microseconds)	Amplitude	Comments	Effect
Bai	2-100			Transcutaneous Posterior Tibial, Dysmenorrhea, frequency not controlled or compared	Efficacious for Dysmenorrhea
Lauretti	85		variable	Transcutaneous Suprapubic, Dysmenorrhea	Efficacious for dysmenorrhea pain and QOL
Lee	100	100		TENS lower abdomen and thermotherapy for Dysmenorrhea	Efficacious for dysmenorrhea pain and QOL
Buffenoir	100-200	1.4-8.7		Implanted spinal cord stimulation for pudendal neuralgia	Efficacious for decreasing pain
Comiter	16	210		Sacral nerve stimulation, Interstitial cystitis	Effective to reduce pain
Ghazwani	14	200		Sacral nerve stimulation, Bladder pain syndrome	Effective to reduce pain

Kaplan	100	95	50	TENS, Dysmenorrhea,	Effective for pain
Kim	20		10	PTENS(Percutaneous electrical nerve stimulation), chronic pelvic pain	May be helpful for pain but was not statistically significant
Maher	15	210		Percutaneous S3 Sacral Nerve Stimulation, Interstitial Cystitis	Improved pelvic pain, nocturia
Schneider	80	150		Transcutaneous penile electrodes, pain scale and QOL	Reduced pain and increased QOL
Tugay	120	100		Transcutaneous Lower Back, Dysmenorrhea	Not statistically significant for dysmenorrhea
Vallinga	80	50-180		TENS (Location not specified), Vestibulodinia	Reduced Vulvar pain
Van Balken	20	200	0-10	Percutaneous, Posterior tibial nerve, Chronic pelvic pain	Reduced pain and improved QOL

The goal of the current study is to determine which pulse rate (Hz) is the most effective to use in posterior tibial transcutaneous electric nerve stimulation for treating pelvic pain given a set location (posterior tibial nerve) and Pulse Width (200 microseconds) on continuous stimulation.

Specific Aim: To determine if a low (Group 1, 20 Hz), medium (Group 2, 50Hz), or high (Group 3, 100 Hz) pulse rate (frequency) used in posterior tibial TENS is better in improving pelvic pain (as measured by decreased Visual Analog Scale (VAS) scores and improved pain, urinary and QOL scales on the validated Genitourinary Pain Index (GUPI).

Hypothesis: A high frequency (100 Hz) used in TENS will show the most improvement in pelvic pain compared to low and medium frequencies.

B. STUDY DESIGN

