All subjects will be analyzed according to the intention-to-treat [ITT] principle. A participant will be considered evaluable and will be included in the intention-to-treat analysis if the participant has documented at least 8 sessions of their designated TENS treatment (about 4 times a week of TENS therapy). Analyses that take into account the actual treatment received (e.g., non-compliance, etc.) will be carried out as a secondary analysis (per protocol [PP] analysis).

Primary Statistical Objective:

The primary objective of the study is to compare the three TENS treatment groups after two weeks of active treatment, with respect to:

The change in VAS and GUPI pain questionnaires from baseline to after two weeks of

therapy.

The proportion of responders after two weeks of therapy.

Secondary Statistical Objectives:

Secondary objectives include comparison of the three treatment groups with respect to the rating of VAS and GUPI scores, separately, over time (by weekly diary entries). Analysis will be carried out to determine if there are time-dependent changes in questionnaire scores across the three TENS treatment groups. Urinary symptoms and individual pain site questions will be noted.

Pairwise comparisons of TENS groups will also be carried out to compare each arm with one another using Tukey's multiple comparison tests.

We will again collect data at 1,2-, and 3-months post-trial, asking how much the TENS has been used, to assess durability.

Outcome Variables and Schedule of Assessments:

The primary outcome variable of interest is participant's percentage change in VAS and GUPI from before treatment to the end of 2 weeks of active TENS. Also evaluated will be the response to treatment each week during the 14-day TENS therapy period and the 2 weeks of observation. A participant is said to have a favorable response to the treatment if he/she has a decrease of at least 2 points on the VAS or 1 point on the GUPI question #9 from baseline to after two weeks of TENS therapy. Change in outside interventions will not be permitted during the study but stable therapies will be maintained (e.g., medications).

Demographics and participant characteristics will be collected at baseline (age, gender, medical history, surgical history, current medications, site of pain, duration of chronic pelvic pain). The following outcomes will be measured at baseline, at each week, and at 3 months after the TENS therapy month:

- VAS Weekly Scores
- GUPI Weekly Scores

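### With three arms, single-step Tukey (or Bonferroni) is valid but stricter than a 5% family error needs once one pair is rejected; a step-down version would separate 100 Hz from both other frequencies more often.

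*Combined protocol and SAP*

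**What the plan says.** Section A states the scientific target: "Hypothesis: A high frequency (100 Hz) used in TENS will show the most improvement in pelvic pain compared to low and medium frequencies".

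Section D names pairwise methods for means in four places:

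- Statistical Methods, primary objectives: Tukey after the one-way ANOVA of relative change in genitourinary symptoms.
- Statistical Methods, primary objectives: Tukey again after the repeated measures ANOVA of VAS.
- Statistical Methods, secondary objectives (week-to-week analysis): "Adjusted pairwise comparisons (Tukey or Bonferroni method) will be used to compare treatment groups to one another".
- Secondary Statistical Objectives: "Pairwise comparisons of TENS groups will also be carried out to compare each arm with one another", by Tukey.

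As named, all are single-step procedures. No step-down or closed procedure is mentioned.

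Sample Size Considerations bases power on "ANOVA with 2-tailed alpha of 0.05" and a difference of "at least one within-group standard deviation of the change in score at 14 days". It reports: "With 21 participants per group the power is estimated at 81" percent. That figure is for the overall ANOVA, not for any pair.

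**The concern.** Showing that 100 Hz is better than both 20 Hz and 50 Hz takes two pairwise results. A single-step method holds all three pairs to the threshold needed when all arms are equal, even after the data have rejected that possibility. The second of the two results is then harder to obtain than the 5% guarantee requires.

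At stake is power for the stated hypothesis in a trial of 75, where extra participants are costly and a change of wording is not.

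**Working it through.** **Inputs.** Three arms with equal allocation (Section D, Randomization: "Subjects will be randomly assigned with equal probability to one of the three study groups"); two-sided 5%; 21 evaluable per arm; a 1 SD difference in the change score. The plan does not give the pattern of the three means, so several are tried, written as 20/50/100 Hz in within-group SDs. Normal data, equal n and common variance are assumed.

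**1. The plan's own figure.** ANOVA power comes from the noncentral F with 2 and 60 df and noncentrality n × Σ(mean − grand mean)².

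- 0/0.5/1: 21 × (0.25 + 0 + 0.25) = 10.5, power 81.5%. This reproduces the stated 81%.
- 0/0/1: 21 × (1/9 + 1/9 + 4/9) = 14, power 91.5%. This does not.

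**2. Critical values at 60 df.** Each pair uses t = difference / (pooled SD × √(2/21)), and √(2/21) = 0.3086.

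| Method | Critical absolute t | Smallest significant difference (SD) |
|---|---|---|
| Bonferroni | 2.463 | 0.760 |
| Tukey, q/√2 | 2.403 | 0.742 |
| Unadjusted | 2.000 | 0.617 |

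**3. Why the second step is allowed.** If any two of the three pairwise nulls are true, all three arms are equal. The closed family is therefore the global null plus three single pairs. Step one tests the global null with the Tukey range: the largest absolute t must exceed 2.403. Step two tests each remaining pair at 2.000.

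- All arms equal: a false rejection needs step one to pass, which happens 5% of the time.
- One pair equal: its false rejection needs its own absolute t to exceed 2.000, which happens at most 5% of the time.
- No Tukey rejection is lost, because 2.403 exceeds 2.000.

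**4. Probability that 100 Hz is significantly better than both others** (simulation, at least 2,000,000 trials per scenario):

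| n per arm | Pattern | Tukey | Step-down | Gain (points) |
|---|---|---|---|---|
| 21 | 0/0/1 | 68.5% | 80.4% | 11.9 |
| 21 | 0/0.25/1 | 47.0% | 61.6% | about 15 |
| 21 | 0/0.5/1 | 21.5% | 34.1% | about 12.5 |
| 21 | 0/0/0.5 | 10.6% | 18.3% | 7.6 |
| 21 | 0/0/0.75 | 35.2% | 49.1% | 13.9 |
| 21 | 0/0/1.25 | 90.8% | 95.7% | 4.9 |
| 21 | 0/0/1.5 | 98.5% | 99.5% | about 1 |
| 20 | 0/0/1 | 65.3% | 77.8% | 12.5 |
| 25 | 0/0/1 | 78.9% | 88.1% | about 9 |

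The 20-per-arm row is 25 × (1 − 0.20), from "We propose to randomize 25 per group assuming the dropout rate may be as high as 20" percent. Bonferroni at 21 per arm gives 66.2% for 0/0/1 and 19.9% for 0/0.5/1, below Tukey in both.

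**5. What does not change, and what does.** The chance of at least one rejection is the same for Tukey and step-down (90.8% for 0/0/1). With all arms equal, family error is 5.0% for both and 4.35% for Bonferroni. With 20 Hz equal to 50 Hz and 100 Hz different, false separation of 20 from 50 Hz is 1.9% with Tukey and 5.0% with step-down.

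**6. The form of step-down matters.** For 0/0/1, plain Holm reaches only 72.3% and loses a Tukey rejection in 1.1% of trials. Unadjusted tests after a significant F test gain 12.9 points over Tukey but lose a Tukey rejection in about 0.5% of trials. Only the range-based version keeps every Tukey rejection.

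**The case against.** The strongest reply is that nothing here is an error. Tukey is valid, is exactly 5% when all arms are equal, and gives simultaneous intervals that agree with its tests. That stands: this is a gain in efficiency, not a correction of a mistake.

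Three stronger readings are tempting, and the documents do not support them.

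- *The step-down costs nothing in error control.* It keeps the 5% maximum but uses slack that Tukey leaves. False separation of two equal arms rises from 1.9% to 5.0%. VAS and GUPI change are both primary and no control across them is stated. If 20 and 50 Hz were equal on both, the upper bound on a false 20 versus 50 Hz claim would go from 1.9 + 1.9 = 3.8% to 5.0 + 5.0 = 10.0%.
- *The trial succeeds only if 100 Hz beats both others.* The hypothesis points that way, but the primary objective is to compare the three groups, and the explicit arm-to-arm objective is listed as secondary. No success rule is stated.
- *The responder analysis is defective because no pairwise test is named.* The plan has an overall chi-square or Fisher test and assumes about 40% response in every arm. It promises no pairwise responder claim, so this is absent detail at most.

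It is also fair to say that the quoted Bonferroni alternative belongs only to the secondary weekly analysis. Changing that sentence alone would leave the primary comparisons untouched and the plan inconsistent.

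**Conclusion.** The point holds as an efficiency improvement. At the plan's 21 per arm and a largest gap of 1 SD, step-down adds about 12 to 15 points to the chance of separating 100 Hz from both other arms, with the same 5% maximum family error per outcome and time point. For 0/0/1, step-down with 21 per arm (80.4%) slightly exceeds single-step Tukey with all 25 retained (78.9%). Other effects give smaller gains, 5 points or less once both gaps reach 1.25 SD.

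The figures rest on normal data, equal n and common variance for the two-week change. They do not carry over directly to the repeated measures models, because the within-person correlation is not given.

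A reader might infer that the stated 81% is wrong, or that step-down makes the hypothesis well powered. Neither follows. The 81% reproduces for the overall ANOVA, and under that same pattern the power to separate 100 Hz from both others is still only 34.1% after the change.

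**What to change.** In the two primary Tukey sentences and the secondary pairwise sentence of Statistical Methods, and in the Tukey sentence of Secondary Statistical Objectives, state:

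*Each pair is tested at the Tukey-adjusted 5% level; if at least one pair is significant, the remaining pairs are tested at unadjusted two-sided 5%.*

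Delete the Bonferroni alternative for comparisons of means; this also closes a choice now left open until analysis. Keep Tukey simultaneous intervals for display, with a footnote that they may cover zero for a pair declared different at the second step. Make the change before the data are analysed.

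The cost is wording in four places, the possible mismatch between interval and test, and the rise from about 1.9% to 5.0% in false separation of two equal arms when the third differs. No participants or procedures are added. Multiplicity across VAS, GUPI and response, and across weeks, needs its own rule. Pairwise responder tests are optional and not part of this change.

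### The plan has no rule for naming the most effective frequency, and its 81% is power for some difference among the arms, not for the hypothesis that 100 Hz beats both others

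*Combined protocol and SAP*

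**What the plan says.** Section A sets a selection aim: "The goal of the current study is to determine which pulse rate (Hz) is the most effective to use". It then names the expected winner: "Hypothesis: A high frequency (100 Hz) used in TENS will show the most improvement in pelvic pain compared to low and medium frequencies". The opening of Section D repeats the aim as the study objective.

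The Primary Statistical Objective is worded more broadly, as a comparison of the three groups on change in VAS and GUPI and on the proportion of responders. Under Statistical Methods, the primary analysis is ANOVA with Tukey comparisons for relative change in genitourinary symptoms, repeated measures ANOVA with Tukey comparisons for VAS, and a chi-square or Fisher test for response. The secondary objectives add: "Pairwise comparisons of TENS groups will also be carried out to compare each arm with one another using Tukey's multiple comparison tests".

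Sample Size Considerations bases the numbers on "ANOVA with 2-tailed alpha of 0.05", for a difference among the three groups in VAS change of "at least one within-group standard deviation of the change in score at 14 days". The result is "With 21 participants per group the power is estimated at 81" per cent, and then "We propose to randomize 25 per group assuming the dropout rate may be as high as 20" per cent. The section does not say where the 50 Hz mean lies between the extremes, and it gives no power for any pairwise comparison.

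**The concern.** Showing that one setting is best among three takes two comparisons, one against each of the others. A significant overall ANOVA does not do this, and neither does 100 Hz beating 20 Hz alone. The plan produces the pairwise results but does not say how they become a declared winner. The candidates are the highest mean, significance against one arm, or significance against both, and the plan does not choose between them before the data are seen.

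Two things follow. A trial in which 100 Hz is ahead of 20 Hz but not separated from 50 Hz has no agreed interpretation and could be written up as support for 100 Hz. And a reader who takes the 81% as power for the hypothesis would be crediting it with the power of a different test.

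**Working it through.** **Inputs from the documents.** Three arms with equal allocation ("Subjects will be randomly assigned with equal probability to one of the three study groups"); alpha 0.05; 21 analysed per arm; a difference of 1 within-group SD in VAS change, read as largest minus smallest mean (all from Section D).

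**Assumption.** The position of the 50 Hz mean is not given, so it is varied. Means are in SD units, with 20 Hz at 0 and 100 Hz at 1.

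**Step 1: reproduce the 81%.** The noncentrality is λ = n Σ(μᵢ − μ̄)². With means 0, 0.5, 1: λ = 21 × (0.25 + 0 + 0.25) = 10.5. With 2 and 60 degrees of freedom, the noncentral F power is 81.5%, which matches. With 50 Hz equal to either extreme, λ = 21 × (1/9 + 1/9 + 4/9) = 14 and the power is 91%. At 0.25 or 0.75, λ = 11.375 and the power is 85%. Of the spacings tried, only halfway reproduces the stated figure for the ANOVA.

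**Step 2: power for the hypothesis.** 100 Hz beats both others when (M₁₀₀ − M₂₀) and (M₁₀₀ − M₅₀) each exceed c × s × √(2/21), with s the pooled SD on 60 degrees of freedom and √(2/21) = 0.309.

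- Tukey: c = 3.399/√2 = 2.403, so each observed gap must exceed about 0.74 SD.
- Unadjusted two-sided 0.05: c = 2.000, so each gap must exceed about 0.62 SD.

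With 50 Hz halfway, the true gap between 100 and 50 Hz is 0.5 SD, below both thresholds. Simulated results at 21 per arm:

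| 50 Hz mean (SD above 20 Hz) | Overall ANOVA | 100 Hz beats both, Tukey | 100 Hz beats both, each at 0.05 | 100 Hz has highest observed mean |
|---|---|---|---|---|
| 0 | 91% | 68% | 82% | over 99% |
| 0.25 | 85% | 47% | 63% | 99% |
| 0.5 | 81% | 22% | 35% | 95% |
| 0.75 | 85% | 6% | 12% | 79% |
| 1 (100 Hz not truly best) | 91% | 1% | 2.5% | 50% |

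In the halfway case, Tukey power is about 20% at 20 per arm and 27% at 25 per arm, so dropout changes little.

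**Step 3: what an unstated rule could allow.** Suppose 50 Hz equals 100 Hz and the winner is taken to be the highest mean after a significant ANOVA. The ANOVA is significant in 91.5% of trials and the two top arms are equally likely to lead, so 100 Hz is named best in 91.5%/2, or about 46%, although no single best exists.

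**Step 4: error of the two-comparison rule.** If 100 Hz is no better than one of the other arms, the claim needs that comparison to be significant in favour of 100 Hz, which happens at most 2.5% of the time. Requiring both comparisons cannot raise this, so no multiplicity penalty is needed. Applied to any arm, with two arms tied at the top, either can be wrongly named: 2 × 2.5% = 5%. Simulation agreed, with at most about 5% in the cases run.

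**The case against.** The strongest reply is that the plan already contains what is needed. The 81% is openly labelled as ANOVA power, and it fits the Primary Statistical Objective, which is to compare the three groups. Tukey comparisons are in the primary analysis, not only among the secondary objectives. They would show when 100 Hz was not separated from 50 Hz, and they would wrongly put 100 Hz above both in only about 1% of trials when 50 Hz is equally good. All of this stands. It would be wrong to infer that the plan lacks pairwise tests or misdescribes its power. What is missing is the step from the pairwise results to a named frequency, and the power for that step.

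A reader might also take 22% as the trial's true power. The documents do not support that. The halfway position is inferred from the 81%. Because it is the least favourable spacing for the overall test at a fixed range, it may be a cautious sizing convention and not a forecast for 50 Hz. For the same reason, one cannot say that most positive trials would fail to separate 100 from 50 Hz. The 22% also presumes a rule, Tukey significance against both arms, that the plan does not state. If the intended rule were simply the highest mean, 100 Hz would be picked about 95% of the time in that scenario. That rule is open to the plan's authors, but they have not stated it, and with a significant ANOVA it carries the 46% figure above.

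Finally, VAS, GUPI and response are all listed as primary. Placing the rule on VAS is a choice, made because the trial was sized on VAS.

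**Conclusion.** The point holds in limited form. The aim and hypothesis are to name a best frequency; the plan has no rule for doing so and gives no power for it. The 81% is sound for the test it describes. At every position of 50 Hz tried, the power for 100 Hz to beat both others is below the ANOVA power, so the gap does not depend on the inferred spacing; only its size does. By Tukey it runs from about 68% down to 6% as 50 Hz moves from equal to 20 Hz up to 0.75 SD above it, with 22% at halfway.

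These figures assume a 1 SD range, 21 analysed per arm, normal data with a common SD, and 100 Hz truly best. This is an inexpensive improvement to a usable analysis, not a fault that invalidates it.

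**What to change.** Add to the primary VAS analysis: a frequency is declared most effective only if its improvement exceeds that of each of the other two, each at two-sided 0.05, without Tukey adjustment; otherwise the report states which frequencies were not distinguished. The rule should apply to any of the three arms, since the aim asks which frequency is best and not only whether 100 Hz is. It should also name the VAS rating it uses, because the Appendix lists four. Keep the ANOVA, Tukey, GUPI and responder analyses as planned.

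In Sample Size Considerations, keep the 81% as power for the overall ANOVA and add the power for the hypothesis under this rule at 21 per arm: about 82% if 50 Hz equals 20 Hz, 63% if 0.25 SD above it, 35% if halfway and 12% if 0.75 SD above. This is higher than Tukey gives for the same claim at every one of these positions (35% against 22% at halfway).

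The cost is wording only and no extra patients. The downside is a less favourable stated power for the headline claim. The rule does not make the trial large enough if 50 Hz is close to 100 Hz; for scale, 80% power by Tukey with 50 Hz halfway would take about 83 per arm.
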